### 9.7. Treatment Compliance

Patient compliance with study medication will be assessed at each visit. Compliance will be assessed by direct questioning, review of diary, and counting returned tablets. Deviations from the prescribed dosage regimen should be recorded in the “Study treatment: modifications” form.

For patients who are significantly noncompliant (<80% or >120% of expected study drug taken in a visit interval), investigative sites must counsel patients on the importance of study drug compliance and drug accountability. Patients who are consistently out of the compliance range may be discontinued. A Lilly representative should be contacted upon the second instance of treatment noncompliance.

The following procedures will be employed to ensure appropriate drug accountability:

- Drug accountability will be emphasized at the start-up meeting.
- Drug accountability will be monitored throughout the study.
- Each patient should be instructed to return all study-drug packaging and unused material to the study site at each visit. The study site will keep a record of all drug dispensed to and returned by the patients throughout the study. Study site personnel will return or destroy (as requested) all unused study drug for all patients.

Patients will keep a study diary to document that they are taking LY2157299/  
LY2157299-matched placebo and sorafenib correctly.

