### **12.2.5. Treatment Compliance**

The number of dose omissions, reductions, delays, number of cycles received, and dose intensity will be summarized for all treated patients per treatment arm. A summary of treatment compliance will be generated using information from drug accountability records and the patient diary. The number of tablets taken relative to the number expected to be taken will be summarized by cycle and treatment arm.

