6.7. Treatment Compliance

Subject compliance with study medication will be assessed by reconciling the number of tablets of each tablet strength dispensed at the beginning (or during in the event of a prescribed dose reduction) of each cycle with the number of tablets of each strength returned at the end of the cycle. This will be compared with the number of days for each prescribed dose in the visit interval (exposure days). The number of tablets of each tablet strength taken relative to the number expected/planned to be taken will be summarised for each cycle and overall for each patient.

Details of how treatment compliance summaries are created are listed in Section [6.12.1](#).

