6.12. Safety Analyses

6.12.1. Treatment Compliance and Dose Intensity

The assigned dose of LY2157299 (or matched placebo) for every patient is 300 mg/day and the assigned dose for sorafenib is 800 mg/day for all patients in the combination arms. A prescribed dose is the dose the patient is prescribed to take in each cycle, including adjustments due to dose reductions or omissions within a cycle if prescribed by the investigator.

Treatment compliance is defined by the patient taking the study drug in mg as prescribed.

Dose intensity is expressed as a percentage of actual daily dose (mg) divided by assigned daily dose (mg) across all cycles, including the last cycle that may have been less than 28 days.

Treatment compliance and intensity information for LY2157299 (or placebo) will use collected pill counts of each tablet strength (150 mg and/or 80 mg if dose is reduced) at each cycle and the date of first dose and date of last dose in every cycle and study treatment discontinuation date. The pill counts will determine the extent of patient exposure to study drug. Similarly, treatment compliance and intensity information for sorafenib will use collected pill counts (tablet strength of 200 mg).

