6.12.1.3. Derivations

Subject compliance with study medication will be assessed by reconciling the number of tablets of each tablet strength dispensed at each cycle with the number of tablets of each strength returned at each subsequent cycle through the end of the study treatment. The number of tablets of each strength will be multiplied by the tablet strength to give the **actual total drug taken** in mg. (Note: This amount could alternatively be derived by taking the sum of the actual days dosing occurred (subtracting omitted days from the dosing interval) multiplied by the actual dose per administration and frequency in each dosing interval). This will be compared with the **prescribed total drug taken** by calculating the number of tablets of each strength expected to be taken (prescribed tablets) multiplied by their tablet strength. The prescribed total dose is based on the days for each prescribed daily dose in the dosing interval (exposure days), accounting for any prescribed dose adjustments (delays, omissions, or reductions). The total drug taken relative to the total prescribed will be summarised for each cycle and overall for each patient. A patient will be considered compliant with the study therapy protocol if the total drug taken indicates the patient took between 80% and 120% of the planned LY2157299 dose in mg during the cycle of study therapy.

Dose intensity takes the total drug taken (mg) (from above) in the study divided by the number of days on study treatment (that is, **average actual daily total** in mg) compared to the **assigned total drug** (mg) divided by the **expected number of days on study**, and expressed as a percentage. The assigned total drug is calculated from the sum of the number of cycles completed times the expected number of days of dosing in each cycle (for example, for LY2157299, 13.5 for cycle 1, 14 for every other completed cycle and the number of exposure days of the last cycle on treatment) multiplied by the assigned daily dose at Cycle 1 (for example, for LY2157299, 300 mg). The expected number of days from first dose to study treatment discontinuation is the number of cycles completed times 28 (the expected cycle length) plus the number of days prior to study treatment discontinuation in the last cycle. Dividing assigned total dose by the expected number of days prior to study treatment discontinuation gives the expected daily dose in mg. This calculation allows for dose delays.

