The dose intensity per patient will be summarised using descriptive statistics.

The following compliance and dose intensity definitions ([Table JBAS.6.5](#)) will be used to calculate compliance and intensity for each cycle and overall for each patient:

Table JBAS.6.5. Compliance and Dose Intensity Definitions

Term	Definitions or Rule
Compliance rate (%)	100 x actual drug taken (mg) / total drug (mg) prescribed Calculated for each cycle and overall for each patient
Dose Intensity (%)	100 x actual daily dose (mg) / assigned daily dose (mg) Calculated for each cycle and overall for each patient Note: Daily dose here is determined by assigned or actual cycle length, not just the daily dose given in the dosing period
Components required for calculations above	Definitions or Rule
Total actual drug taken (mg)	Per patient, per cycle, equal to ((the number of tablets dispensed – number of tablets returned)*tablet strength) summed across tablet strength Per patient, the total drug taken per cycle summed over all cycles.
Prescribed exposure days	Days in the dosing interval – days omitted due to non-compliance Note: reasons due to non-compliance are any reasons for an omitted dose that are not due to adverse event (AE) (for example, patient decision or scheduling conflict)
Total expected (prescribed) drug (mg)	Per patient, per cycle: sum of (prescribed exposure days x daily prescribed dose) across different prescribed daily doses Daily prescribed dose is taken from 'Cycle 1 Day 1 Dose 1' and 'Study Treatment Changes' clinical (case) report forms (CRFs) Per patient, the total prescribed drug per cycle summed over all cycles
Total Assigned Drug (mg)	Per patient, per cycle: LY2157299: Sum of (expected days exposure in cycle*300) where expected days exposure in Cycle 1=13.5, expected days exposure in Cycle 2+ = 14 and expected days exposure in the last incomplete cycle = date of last dose in cycle – date of first dose of cycle +1 Per patient, the total assigned drug per cycle summed over all cycles Sorafenib: Sum of (expected days exposure in cycle*800) where expected days exposure in Cycle 1 is 27.5, expected days exposure in Cycle 2+ = 28 and expected days exposure in the last incomplete cycle = date of last dose in cycle – date of first dose of Cycle +1 Per patient, the total assigned drug per cycle summed over all cycles

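### SAP Table JBAS.6.5 takes patient-choice omissions out of the compliance denominator, contrary to SAP 6.12.1 and 6.12.1.3, so recorded self-omission inside the dosing interval scores 100%; Appendix 1 check [3] is inverted

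*SAP*

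**What the plan says.** Table JBAS.6.5 sets compliance at 100 times mg taken over mg prescribed, and mg prescribed at prescribed exposure days times the daily prescribed dose. Prescribed exposure days are the length of the dosing interval less "days omitted due to non-compliance". The note to that row says "reasons due to non-compliance are any reasons for an omitted dose that are not due to adverse event (AE" and gives patient decision and a scheduling conflict as examples. The sentence introducing the table makes these the working definitions.

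The surrounding SAP text differs:

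- SAP 6.12.1 describes the prescribed dose as "including adjustments due to dose reductions or omissions within a cycle if prescribed by the investigator".
- SAP 6.12.1.3 bases the prescribed total on exposure days, "accounting for any prescribed dose adjustments (delays, omissions, or reductions".
- SAP 6.7 has tablets "taken relative to the number expected/planned to be taken will be summarised for each cycle and overall for each patient". Protocol 12.2.5 says: "The number of tablets taken relative to the number expected to be taken will be summarized by cycle and treatment arm". Neither states how omissions enter the expected number.

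The thresholds are the same in both documents. Protocol 9.7 calls a patient "significantly noncompliant (<80% or >120% of expected study drug taken in a visit interval", and SAP 6.12.1.3 calls a patient compliant if "the patient took between 80% and 120% of the planned LY2157299 dose in mg during the cycle of study therapy". SAP Appendix 1 lists cycles outside those limits as significant violations. SAP 6.12.9 allows patients with significant violations to be left out of the per-protocol population, whose use for efficacy is optional (Table JBAS.6.2). SAP 6.12.1.2 sends every missed dose to an omission form, whether the omission was prescribed or the patient's own.

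Four nearby entries also fail to match their sources:

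- Appendix 1 check [3] identifies a violation when baseline measurements show a measurable tumor; inclusion criterion [3] requires measurable disease.
- Check [4] flags age 18 or below; inclusion criterion [4] admits patients from age 18.
- The ANC and platelet check names central laboratory data; protocol Attachment 2 and SAP Table JBAS.6.6 assign hematology to the local laboratory.
- Table JBAS.6.4 gives 111 sorafenib tablets for Cycle 1; Table JBAS.6.5 gives 27.5 expected days.

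**The concern.** A compliance measure is meant to detect doses that a patient was told to take and did not. The table removes exactly those doses from the denominator once they are recorded, so they cannot lower the ratio. The narrative sections remove only what the investigator prescribed. A programmer following the table and one following the text would produce different percentages from the same data.

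The score also comes to depend on paperwork. Within a fixed 14-day window, the same missed doses lower compliance if the site leaves the omission form blank and do not lower it if the site completes the form. What is at stake is the compliance percentage, the Appendix 1 violation listing built on it, and membership of a per-protocol set if one is used.

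**Working it through.** **Inputs.** LY2157299 is assigned at 300 mg/day in 150 mg tablets, and sorafenib at 800 mg/day in 200 mg tablets (SAP 6.12.1). Dosing days are 13.5 in Cycle 1 and 14 later for LY2157299, and 27.5 and 28 for sorafenib (Table JBAS.6.5).

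**The plan's own counts (Table JBAS.6.4).** LY2157299: 13.5 × 300/150 = 27 and 14 × 300/150 = 28, both as stated. Sorafenib from Cycle 2: 28 × 800/200 = 112, as stated. Sorafenib Cycle 1: 27.5 × 800/200 = 110, against 111 stated.

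**Recorded self-omission of k days inside a 14-day interval, Cycle 2 onward.** Mg taken = (14 − k) × 300.

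- Table rule: denominator (14 − k) × 300, so compliance is 100% for any k below 14. At k = 7 it is 2100/2100. At k = 14 it is 0/0, undefined.
- Narrative rule: denominator 14 × 300 = 4200, so compliance is (14 − k)/14: 85.7% at k = 2, 78.6% at k = 3, 50% at k = 7.

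SAP 6.12.1.3 also allows mg taken to be derived from dosing days net of omitted days. With that numerator, and only non-AE omissions, numerator and denominator are the same expression.

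**Where the narrative rule would list a patient.** By single dose, Cycle 2 onward: 23/28 = 82.1% (5 missed) and 22/28 = 78.6% (6 missed). Cycle 1: 22/27 = 81.5% (5 missed) and 21/27 = 77.8% (6 missed). Six missed doses therefore trigger the listing in either cycle. Under the table rule, on the conditions above, no number does.

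**Same doses missed but not recorded, fixed 14-day window.** Nothing is subtracted, so 7 days missed gives 2100/4200 = 50%.

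**Interval ending at the last dose.** The SAP does not define the dosing interval, and the form dates in SAP 6.12.1.2 permit this reading. If the patient chooses to omit the last k days, the interval is already 14 − k days and the table subtracts k again. With pill counts as numerator, compliance is (14 − k)/(14 − 2k):

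- k = 2: 3600/3000 = 120%
- k = 3: 3300/2400 = 137.5%, listed as over-compliance
- k = 7: 2100/0, undefined

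**Mixed omissions.** With 7 self-omitted and 3 AE days in a 14-day interval, 4 × 300 = 1200 mg is taken. The table gives 1200/2100 = 57.1%. The narrative rule, with the AE days prescribed, gives 1200/(11 × 300) = 36.4%.

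**The case against.** The strongest reply is that the table does not hide self-omission in every case. That is correct. A reader might infer that recorded self-omission always scores 100% and can never be listed. The documents do not support this: if the interval stops at the last dose, trailing omissions push the score above 100%, and from 3 days it is listed, though as over-compliance. The 100% result also needs pill counts that match the log, at least one dose taken, and no AE or unrecorded omission in the cycle.

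A reader might also infer that the table generally penalises AE omissions. It does so only if the same dose resumes within the window and the interval is not already net of prescribed omissions (3 days: 3300/4200 = 78.6%). An AE gap followed by a reduced dose falls between two intervals: 5 × 300 + 6 × 160 = 2460 mg both taken and prescribed, or 100%.

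The conflict with SAP 6.7 and protocol 12.2.5 is by implication only, since neither says how omissions are treated.

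There are partial backstops. Monitors check compliance as well as the program; protocol 9.7 has sites use questioning, diaries and tablet counts; and the dosing listing shows tablets and omissions beside the percentage. These make an error visible but do not correct the percentage or the programmatic flag.

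Finally, because eligibility rests on local results by default (protocol 10.4.1), a reader might want Appendix 1 check [6] moved to local data too. The documents do not show that this is feasible: clinical chemistry is assigned to the sponsor-designated or central laboratory, and the check screens only for potential violations.

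**Conclusion.** The contradiction between Table JBAS.6.5 and SAP 6.12.1 and 6.12.1.3 is real. For recorded self-omission inside the dosing interval (a fixed 14-day window, or the same dose resumed), and on the conditions given above, the table returns 100% where the narrative rule returns 50% for 7 of 14 days, and the under-80% flag misses the patient. On the last-dose reading of the interval the table gives a different wrong answer, so neither reading rescues it.

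The reach is limited to the compliance percentage, the violation listing and an optional per-protocol set. Primary OS is analysed on the randomized population, and dose intensity uses assigned drug and actual days, so both are unaffected. It is worth correcting because the rule is wrong as written and cheap to repair.

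Check [3] is inverted: run literally, it flags patients who meet the criterion and passes those who do not, leaving monitoring as the only safeguard. Check [4] affects only patients aged exactly 18. The sorafenib tablet count differs by one (111 against 110, under 1%) and does not enter the table's percentage, which is computed from days and dose.

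**What to change.** In Table JBAS.6.5:

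- Define prescribed exposure days as dosing-interval days less prescribed or protocol-directed omissions only. That covers prescribed AE omissions, and the Cycle 1 Day 14 evening dose omitted for PK sampling unless 13.5 or 27.5 days is already used.
- Keep unprescribed patient omissions in the denominator.
- Define the dosing interval, stating whether it is the planned window or ends at the last dose.

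In Appendix 1:

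- Word check [3] so that a tumor that is *not* measurable is the violation.
- Set check [4] to age below 18.
- Run the ANC and platelet check on the local hematology data.
- Leave check [6] as it is.

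Reconcile the Cycle 1 sorafenib tablet count in Table JBAS.6.4 with the exposure days in Table JBAS.6.5.

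The cost is SAP wording and derivation code, with one thing to confirm first. SAP 6.12.1.2 mentions only dates and times on the omission form, so check that the form also captures the reason, as the table's note implies.

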6.12.1.1. Planned dosing

Patients will be randomly assigned to one of the following arms shown in [Table JBAS.6.4](#).

Table JBAS.6.4. Treatment Regimens

				Number of Tablets Prescribed per Cycle^d
Daily Dose		Schedule	Time of Day	
Arm 1	150 mg BID LY	Daily 14 days on/14 days off	Morning and evening for 14 days ^{a,b} and then paused for 14 days	27 (Cycle 1) 28 (Cycle 2+)
Arm 2	150 mg BID LY ^c plus	Daily 14 days on/14 days off	Morning and evening for 14 days ^{a,b} with sorafenib and then paused for 14 days.	27 (Cycle 1) 28 (Cycle 2+)
	400 mg (2x200mg) BID sorafenib	Daily	Take in the morning and evening for 28 days	111 (Cycle 1) 112 (Cycle 2+)
Arm 3	LY-matched placebo plus	Daily 14 days on/14 days off	Morning and evening for 14 days ^{a,b} with sorafenib and then paused for 14 days.	27 (Cycle 1) 28 (Cycle 2+)
	400 mg (2x200mg) BID sorafenib	Daily	Take in the morning and evening for 28 days	111 (Cycle 1) 112 (Cycle 2+)

Abbreviations: BID = twice daily; LY = LY2157299; PK = pharmacokinetic.

Note: For patients who will have a Day 15 PK sample taken, the evening dose on Day 14 will be omitted to allow for a 24-hour time period between the Day 14 morning dose and the Day 15 PK sample.

^a In extenuating circumstances, the “on-study-drug” window for LY2157299 is allowable from Day 10 to Day 14.

^b Both study drugs should be taken on an empty stomach, at least 1 hour before a meal.

^c LY2157299 dose will be defined based on the results of the H9H-MC-JBAK study. Dose will either be 80 or 150 mg BID.

^d Assuming no prescribed omissions or adjustments.

LY2157299 300 mg/day will be administered orally 150 mg BID in 150-mg tablet form (300 mg total daily dose). A cycle (28 days) will be defined as an intermittent dosing regimen of 14 days of LY2157299 followed by 14 days without LY2157299 administration. All patients should not receive more than 14 consecutive days of LY2157299 dosing (28 tablets).

Sorafenib 800 mg/day will be administered orally 400 mg BID (2 tablets \times 200mg BID) for a 800 mg total daily dose. Sorafenib dosing will occur consistently throughout the 28-day cycle. All patients assigned to the combination arms should not receive more than 28 consecutive days of sorafenib dosing (112 tablets).

During Cycle 1 only, all patients should omit the Day 14 evening dose to ensure a 24-hour PK assessment. Visit/cycle start dates may vary \pm 3 days due to holidays, inclement weather, etc.

Planned dose adjustments and delays

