Total days of actual exposure at each prescribed dose	Per patient, per cycle, per dose: Days of exposure = sum (date of last dose – date of first dose +1) taken from the chronology of dates from 'Cycle 1 Day 1 Dose 1', 'Study Treatment Changes' and 'Study Treatment Last Dose' CRFs The total days of actual exposure over all doses prescribed during a cycle should be: LY2157299: 13.5 for Cycle 1 and 14 for Cycle 2+ (unless planned omission or incomplete last cycle). Sorafenib: 27.5 for Cycle 1 and 28 for Cycle 2+ (unless planned omission or incomplete last cycle). Total days of actual exposure for a patient in the study is the sum of exposure days across all cycles

Compliance and Dose Intensity Definitions

Term	Definitions or Rule
Total days expected to be on study given number of cycles completed and length of last cycle on study treatment (excludes any dose delays)	
Per patient, per cycle: 28 for all completed cycles and (date of study treatment discontinuation- date of first dose in last cycle+1) for the last cycle on study treatment
 
Per patient:
 
Days expected to be on study=(number of started cycles-1)*28 + (date of study treatment discontinuation- date of first dose in last cycle+1)

Total actual days on study (includes dose delays)	
Per Patient, per cycle: Date of first dose in cycle (x+1) – date of first dose in cycle (x) for all cycles except the cycle started.
 
Number of days on last cycle started = date of study treatment discontinuation – date of first dose in last cycle
 
Per patient: Date of study treatment discontinuation – date of first dose +1 (should be equivalent to the sum of days on study across cycles)

Assigned daily dose	
Per patient, per cycle: Total assigned drug/total expected days for each cycle
 
Per patient: Total assigned drug across cycles/total days expected to be on study across cycles

Actual daily dose	
Per patient, per cycle: Total actual drug taken/total actual days for each cycle
 
Per patient: Total actual drug across cycles/total actual days on study across cycles
 
Note: This is NOT the same as the sum of the assigned daily dose per patient per cycle/number of cycles.

Using the compliance and dose intensity derived for each patient as above, compliance and dose intensity will be summarised for LY2157299 and sorafenib by the following listing and table:

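### SAP dose intensity counts last-cycle assigned drug only to the patient's own last dose, so a stop and discontinuation within that cycle can score 100% whatever scheduled drug was missed

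*SAP*

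**What the plan says.** SAP 6.12.1.3 and Table JBAS.6.5 define dose intensity as actual daily dose over assigned daily dose, as a percentage.

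- **Per-patient assigned daily dose:** "Total assigned drug across cycles/total days expected to be on study across cycles".
- **Per-patient actual daily dose:** "Total actual drug across cycles/total actual days on study across cycles".
- **Assigned drug, last incomplete cycle:** for both drugs the table uses "expected days exposure in the last incomplete cycle = date of last dose in cycle" minus the first dose date of the cycle, plus 1, times 300 mg or 800 mg. The narrative agrees for LY2157299: 13.5 days in Cycle 1, then "14 for every other completed cycle and the number of exposure days of the last cycle on treatment".
- **Expected days, last cycle:** study treatment discontinuation date minus first dose date of that cycle, plus 1.
- **Actual days, last cycle:** "Number of days on last cycle started = date of study treatment discontinuation" minus the first dose date of that cycle, with no +1. The per-patient total of actual days does carry +1, and the table says it "should be equivalent to the sum of days on study across cycles".
- **Sorafenib tablets (Table JBAS.6.4, both sorafenib arms):** "111 (Cycle 1) 112 (Cycle 2" and later cycles.

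A note in Table JBAS.6.5 says that daily dose depends on cycle length, assigned or actual, and not only on the dose given during the dosing period. The text of 6.12.1.3 adds that the calculation allows for dose delays.

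**The concern.** The day counts run to discontinuation, but assigned drug stops at the patient's own last dose. In the last cycle the yardstick therefore shrinks to fit what the patient took. A stop that ends in discontinuation costs nothing in the score, although the SAP says that cycle length sets the daily dose and that delays are allowed for.

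The gap between last dose and discontinuation is realistic. Protocol 9.4.1.1 has patients withdrawn after LY2157299 has been delayed for more than 2 weeks for treatment-related events. Protocol Table JBAS.9.3 has sorafenib discontinued if there is no recovery after a 30-day delay, with an exception for patients deriving clinical benefit.

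At stake is the dose-intensity summary by arm, which protocol 12.2.5 and 12.2.11 and SAP 6.12.1.3 all plan. As defined, it can report full intensity for patients who missed much of their last scheduled course.

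**Working it through.** **The plan's tablet counts first.** Tablets = expected days × daily mg ÷ tablet strength.

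- LY2157299 Cycle 1: 13.5 × 300 / 150 = 27. This reproduces.
- LY2157299 Cycle 2 onward: 14 × 300 / 150 = 28. This reproduces.
- Sorafenib Cycle 2 onward: 28 × 800 / 200 = 112. This reproduces.
- Sorafenib Cycle 1: 27.5 × 800 / 200 = 110, not 111. Protocol Attachment 5 omits the Day 14 evening dose of both drugs; for sorafenib that is 2 × 200 mg, so 112 − 2 = 110. A count of 111 would mean 111 × 200 / 800 = 27.75 days, or half a dose omitted.

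**Overall dose intensity.** Let T be mg taken, A assigned mg, E expected days and D actual days. Then intensity = 100 × (T/D) / (A/E). With no cycle delays, the per-patient formulas give D = E, so intensity = 100 × T/A.

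Take LY2157299 with earlier cycles full and undelayed, last dose on Day 5 of the final cycle, and discontinuation on Day 22. The last cycle adds 5 × 300 = 1,500 mg to both T and A, so T = A and the score is 100%. Against drug scheduled to discontinuation (13.5 × 300 = 4,050 mg in Cycle 1, 14 × 300 = 4,200 mg later):

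- Stop in Cycle 1: 1,500 / 4,050 = 37.0%
- Stop in Cycle 2: (4,050 + 1,500) / (4,050 + 4,200) = 5,550 / 8,250 = 67.3%
- Stop in Cycle 3: (4,050 + 4,200 + 1,500) / (4,050 + 4,200 + 4,200) = 9,750 / 12,450 = 78.3%

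Sorafenib, assuming all study treatment is discontinued on that date: Cycle 1 full (27.5 × 800 = 22,000 mg), last dose Day 5 of Cycle 2 (5 × 800 = 4,000 mg), discontinued Day 22. The SAP gives 26,000 / 26,000 = 100%. On schedule it is 26,000 / (22,000 + 22 × 800) = 26,000 / 39,600 = 65.7%.

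**Ordering.** Compare two patients in a last incomplete cycle after Cycle 1, counting that cycle's LY2157299 only. One takes Days 1–5, omits Days 6–12 and resumes on Days 13–14: 7 × 300 = 2,100 mg taken, 14 × 300 = 4,200 mg assigned, 50%. The other takes Days 1–5 and never resumes: 1,500 / 1,500 = 100%. The patient who took less drug scores higher.

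**Off by one.** Let L be days from first dose of the last cycle to discontinuation, inclusive. Expected days are L and actual days are L − 1, so last-cycle intensity is multiplied by L/(L − 1): 28/27 = 103.7%, 14/13 = 107.7%, 7/6 = 116.7%. It is undefined at L = 1. In the Cycle 2 example the per-patient actual days are 28 + 22 = 50, but the cycle days sum to 28 + 21 = 49, so the stated equivalence fails by one day.

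**The case against.** Intensity while dosed, with discontinuation reported separately, is a defensible measure. Stops are also visible elsewhere: the plan summarises cycles completed, reductions, omissions, delays, reasons for adjustment, and adverse events leading to discontinuation. This limits the damage but does not cure the definition. The SAP does not say that it chose that measure, and its day counts do not end at the last dose.

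The objection also rightly bounds several stronger readings that a reader might infer:

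- **Every toxicity stop scores 100%.** It does not. Omissions followed by a restart, dose reductions and delays between cycles still lower the score, and a LY2157299 stop after its 14 dosing days loses nothing.
- **The missing +1 inflates the reported summary.** SAP 6.12.1.3 names a per-patient intensity summary, and per-patient expected and actual days both carry +1. The inflation reaches per-cycle values, which the table defines, or an overall value built by summing cycle days.
- **The 111 figure moves patients across the 80% compliance limit.** Prescribed drug is built from exposure days times daily dose; no formula takes its denominator from Table JBAS.6.4.
- **Sorafenib given up for toxicity is always hidden, even with discontinuation beyond Day 31.** A cycle lasts at most 31 days, and patients may continue LY2157299 or placebo without sorafenib. If later cycles then start, the loss may be counted. The SAP does not say whether the discontinuation date is per drug.
- **The exploratory analyses in SAP 6.14 are compromised.** That section names dose adjustment, not dose intensity.

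**Conclusion.** The point holds under stated conditions: earlier cycles full and undelayed, the stop and discontinuation in the same final incomplete cycle, and for LY2157299 a stop before its 14 dosing days are complete. Overall dose intensity is then 100% regardless of scheduled drug missed. In the worked LY2157299 case the gap is 63, 33 or 22 percentage points for a stop in Cycle 1, 2 or 3, and it shrinks as completed cycles accumulate. The sorafenib figure also assumes that one discontinuation date covers all study treatment.

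The missing +1 and the 111 are plain errors of smaller consequence. Overall survival and the separate adverse-event, discontinuation and dose-adjustment summaries are unaffected. One might infer that the combination arm is made to look better tolerated, but the documents give no rate of such stops by arm and do not name dose intensity as the measure of lost sorafenib exposure. The definitions should be corrected; the trial's conclusions do not depend on them.

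**What to change.** In Table JBAS.6.5 and the matching text of 6.12.1.3:

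- Set last-cycle expected exposure days, for each drug, to the smaller of (study treatment discontinuation date − first dose date of the cycle + 1) and the planned dosing days. These are 14 for LY2157299 (13.5 in Cycle 1) and 28 for sorafenib (27.5 in Cycle 1). For sorafenib, also deduct the half-day when Cycle 1 discontinuation falls on Days 14–27, since the omitted evening dose then lies inside the period.
- State whether the discontinuation date is per drug or for all study treatment, and use the same date in every day count.
- Add +1 to last-cycle actual days, so that cycle days sum to the per-patient total.

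In Table JBAS.6.4, change 111 to 110 in both sorafenib rows.

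The cost is SAP wording and a small programming change using dates already on the case report forms. Reported dose intensity will become somewhat less favourable. No dosing rule changes.
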